4.2 Screening/Baseline Visit procedures

Screening

The PI will communicate with potential participants to determine whether they fit the inclusion/exclusion criteria and would like to participate in the study. If patients are interested in participating, a signed HIPAA waiver will be obtained to allow the PI to review the individual's medical record and confirm eligibility status. The study baseline period will begin within 2 weeks of enrollment.

Baseline

Written informed consent will be obtained from study participants prior to the implementation of any study procedures. The participant will receive a signed and dated informed consent form. See *Section 10.3.2* for details of consent process. The PI will verify inclusion/ exclusion criteria. A pregnancy inquiry will occur and a complete medical history will be obtained in weeks -4 to -2 of the baseline period. In the one week prior to start (week -1), the following data will be obtained: serum electrolytes, 24-hour urine collection, symptom assessment, and hearing assessment.

4.3 Intervention/Treatment procedures (by visits)

During the 6-week dose titration period (period 1), study drug administration visits will occur every 2 weeks on the first day of the participant's weekly, routinely scheduled HD treatments (i.e. Monday or Tuesday during weeks 0, 2, 4, and 6). During the 12-week follow-up period (period 2), study drug administration visits will occur every 4 weeks on the first day of the participant's weekly, routinely scheduled HD treatments (i.e. Monday or Tuesday during weeks 10, 14 and 18).

Dose-titration (period 1)

Week 0:

A. Participants who are not taking oral furosemide at study entry will receive 2-weeks supply of 80 mg oral furosemide twice daily dosing.

- B. Participants who are taking oral furosemide at study entry will receive 2-weeks supply of his/her prescribed oral furosemide dose.
- C. Participants who are taking another loop diuretic (e.g. bumetanide) at study entry will receive 2-weeks supply of an equivalent dose of furosemide (1mg bumetanide = 40 mg furosemide).

Week 2:

- A. Participants who were not taking oral furosemide at study entry and who tolerated the 80 mg twice daily dose (i.e. no hypokalemia, serious hypotension, symptoms, etc.) will receive 2-weeks supply of 120 mg oral furosemide twice daily dosing.
- B. Participants who were taking oral furosemide at study entry and tolerated the first 2 weeks of dosing will receive 2-weeks supply of furosemide dose 50% higher than initial dose, rounded to the nearest whole tablet strength of existing (i.e. available) furosemide tablet formulations (not to exceed 320 mg/day).
- C. Participants who were taking another loop diuretic at study entry and tolerated the first 2 weeks of furosemide dosing will receive 2-weeks supply of furosemide dose 50% higher than their initial dose, rounded to the nearest whole tablet strength of existing (i.e. available) furosemide tablet formulations (not to exceed 320 mg/day).
- D. Participants who did not tolerate the weeks 0 and 1 dose of furosemide will stop furosemide, and it will not be restarted. See below for parameters for determining intolerance.

Week 4:

- A. Participants who were not taking oral furosemide at study entry and who tolerated the 120 mg twice daily dose (i.e. no hypokalemia, serious hypotension, symptoms, etc.) will receive 2-weeks supply of 160 mg oral furosemide twice daily dosing.
- B. Participants who were taking oral furosemide at study entry and tolerated the last 2 weeks of dosing will receive 2-weeks supply of furosemide dose 50% higher than initial dose, rounded to the nearest whole tablet strength of existing (i.e. available) furosemide tablet formulations (not to exceed 320 mg/day).
- C. Participants who were taking another loop diuretic at study entry and tolerated the last 2 weeks of furosemide dosing will receive 2-weeks supply of furosemide dose 50% higher than initial dose, rounded to the nearest whole tablet strength of existing (i.e. available) furosemide tablet formulations (not to exceed 320 mg/day).
- D. Participants who did not tolerate the weeks 2 and 3 dose of furosemide will return to the prior tolerated oral furosemide dose. See below for parameters for determining intolerance.

Week 6:

- A. Participants who were not taking oral furosemide at study entry and who tolerated the 160 mg twice daily dose (i.e. no hypokalemia, serious hypotension, symptoms, etc.) will receive 4-weeks supply of 160 mg oral furosemide twice daily dosing.
- B. Participants who were taking oral furosemide at study entry and tolerated the last 2-weeks of dosing will receive
 4-weeks supply of that same furosemide dose (not to exceed 320 mg/day).
- C. Participants who were taking another loop diuretic at study entry and tolerated the last 2-weeks of furosemide dosing will receive 4-weeks supply of that same furosemide dose (not to exceed 320 mg/day).
- D. Participants who did not tolerate the weeks 4 and 5 dose of furosemide will return to the prior tolerated oral furosemide dose. See below for parameters for determining intolerance.

As specified in **Section 1.3.1**, occurrence of any of the following events will end dose up-titration: 1) electrolyte abnormalities (serum potassium <3.2 mEq/L, serum magnesium <0.8 mEq/L, and/or serum corrected calcium <7 mg/dL); 2) side effects attributable to furosemide (severe or very severe rash, tinnitus, or hearing change); decrease in Inner Effectiveness of Auditory Rehabilitation (Inner EAR) instrument score by more than 10 points; and/or intradialytic systolic BP <80 mmHg that a study investigator attributes to study drug-induced hypovolemia); and/or 3) patient non-

acceptance (defined as the patient reporting unwillingness to take the study drug). If one of these events occur, the participant will return to the prior tolerated oral furosemide dose. If one of these events occurs at the lowest administered dose, oral furosemide will be stopped and not re-started.

The window for each dose-titration period intervention/treatment visit is -4 to +4 days.

Follow-up (period 2)

Weeks 10 and 14: Participants who tolerated (i.e. no hypokalemia, serious hypotension, symptoms, etc.) and accepted furosemide in period will continue their maximally tolerated period 1 dose during the 12-weeks of follow-up. At weeks 10 and 14, they will receive additional 4-weeks supplies of this furosemide dose.

As specified in **Section 1.3.1**, if a participant has electrolyte abnormalities or other side effects attributable to furosemide in period 2 (i.e. on their period 1 maximally tolerated dose), the dose will be lowered sequentially (i.e. dose de-escalation: $160 \rightarrow 120 \rightarrow 80$ mg twice daily, or, if on alternative dosing due to prior diuretic use, decrease dose by 50%, rounded to the nearest whole tablet strength of existing (i.e. available) furosemide tablet formulations, until tolerated). If side effects persist or if the participant chooses, oral furosemide will be stopped.

Week 19: At the first weekly treatment (i.e. Monday or Tuesday) of study week 19, participants will return all unused study drug to a study coordinator.

The window for each follow-up period intervention/treatment visit is -4 to +4 days.

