1.2 Name and Description of Investigational Product or Intervention

Study intervention: Oral furosemide

The information provided in this section was obtained from Food and Drug Administration (FDA) package insert.¹⁹ Furosemide (Lasix[®]) is a diuretic which is an anthranilic acid derivative. Tablets contain furosemide (active ingredient) and lactose monohydrate NF, magnesium stearate NF, starch NF, talc USP, and colloidal silicon dioxide SF (inactive ingredients). Chemically, it is a 4-chloro-N-furfuryI-5-sulfamoylanthranilic acid. It is available in 20, 40 and 80 mg tablets.

Furosemide is a white to off-white odorless crystalline power. It is practically insoluble in water, sparingly soluble in alcohol, freely soluble in dilute alkali solutions and insoluble in dilute acids.

Mechanism of action: Furosemide inhibits the absorption of sodium and chloride not only in the proximal and distal tubules but also in the loop of Henle. The action on the distal tubule is independent of any inhibitory effect on carbonic anhydrase and aldosterone.

Pharmacokinetics: The onset of diuresis following oral administration is within 1 hour. The peak effect occurs within the first or second hour. The duration of diuretic effect is 6 to 8 hours. In fasted normal men, the mean bioavailability of oral furosemide tablets is 64% of that from an intravenous injection of the drug. The terminal half-life of furosemide is approximately 2 hours. Peak plasma concentrations increase with increasing dose, but times-to-peak do not differ among doses. Furosemide is predominantly excreted unchanged in the urine.

Indications and usage: Furosemide is indicated in adults and pediatric patients for the treatment of edema associated with congestive heart failure, cirrhosis of the liver, and kidney disease. Oral furosemide may also be used in adults for the treatment of hypertension alone or in combination with other antihypertensive agents.

Contraindications: Furosemide is contraindicated in patients with anuria and in patients with a history of hypersensitivity to furosemide.

Dosing and dose changes with rationale

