3.3 Study Duration, Enrollment and Number of Participants

The study duration is 18 weeks and consists of a 6-week dose escalation period (period 1) and a subsequent 12week follow-up period (period 2). Our goal sample size is 36 participants in period 1 with the goal of >30 participants continuing on to period 2. We will recruit up to 40 participants to account for dropout and will recruit additional participants if fewer than 30 participants are eligible for period 2.

All participants will be recruited from the University of North Carolina (UNC)-owned Siler City, Pittsboro, Sanford, Lee County, and Carrboro "Carolina Dialysis" HD clinics. We will screen individuals for eligibility if they selfreport, on average, at least 1-cup urine/day. We selected this threshold based on a recent DOPPS analysis showing an association between self-reported urine volume of ≥1 cup/day and lower interdialytic weight gain (IDWG) and mortality.⁴² Our selection criteria exclude patients unlikely to respond to diuretics (i.e. minimal urine output), patients at increased risk for furosemide side effects (e.g. cirrhosis, electrolyte abnormalities, and concurrent use of interacting medications or substances), and patients likely to have urine output decline during the study (i.e. within the first 60-days of HD therapy). We will recruit patients 1:3, incident (60-180 days on HD): prevalent (>180 days on HD) to ensure study of both populations while accounting for the challenge of recruiting incident patients (e.g. fewer eligible patients, research reticence early in therapy). See **Section 3.4** for participant inclusion and exclusion criteria and **Section 9** for enrollment practices.

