3.4 Study Population

Participant Inclusion Criteria

- Patient self-report of at least 1 cup urine/24-hours⁴²
- Age ≥18 years
- Receipt of thrice weekly in-center HD at a participating clinic (UNC-associated Carolina Dialysis- Carrboro, Siler City, Pittsboro, Sanford, and Lee County)
- ≥60 days receiving in-center HD
- Willingness to take study medication and undergo study testing
- Ability to provide informed consent

Participant Exclusion Criteria

- Known allergy to loop diuretic
- History of poor adherence to HD or medical regimen per nephrologist
- >1 hospitalization in prior 30-days
- Frequent hypotension (systolic BP <80 mmHg at >30% of HD treatments in prior 30-days)²¹
- Cirrhosis per nephrologist
- Hearing disorder per nephrologist
- Serum potassium <3.5 mEq/L, magnesium <1 mg/dL, or corrected calcium <8 mg/dL in prior 30-days
- Taking a non-loop diuretic (e.g. spironolactone, eplerenone, ethacrynic acid, thiazides)
- Taking an aminoglycoside, cisplatin, methotrexate, cyclosporine, ACTH, lithium, phenytoin, or oral/intravenous steroid
- Natural licorice consumption
- Prisoners, patients with significant mental illness
- Pregnant patients and nursing mothers

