4 STUDY PROCEDURES

4.1 Overview (Tables 2 and 3)

All study visits will occur at the participant's dialysis clinic at routinely scheduled HD treatments.

- There will be one study visit during the baseline period.
- Dose escalation period (period 1): Blood samples will be collected weekly at mid-week treatment visits (i.e. Wednesday or Thursday during weeks -1, 1, 2, 3, 4, 5 and 6) prior to scheduled dose initiation or dose titration. Urine samples will be collected twice during the dose escalation period at mid-week treatment visits (i.e. Wednesday or Thursday during weeks -1 and 5). Study drug visits will be conducted every two weeks at the first weekly treatment (i.e. Monday or Tuesday during weeks 0, 2, 4, and 6). This structure was selected so that blood results will be collected and analyzed the week prior to study drug dose titration. As such, test results will be available prior to potential dose titration. Adherence and symptom assessment visits will be conducted weekly at the first treatment of each week (i.e. Monday or Tuesday during weeks 1, 2, 3, 4, 5 and 6). Hearing

assessments will be conducted every two weeks at the first weekly treatment (i.e. Monday or Tuesday during weeks 2, 4, and 6).

- Follow-up period (period 2): Blood samples will be collected at mid-week treatment visits every 4 weeks (i.e. Wednesday or Thursday during weeks 9, 13 and 17). Study drug visits will be conducted at the first treatment of each of the subsequent weeks (i.e. Monday or Tuesday during weeks 10 and 14). As in the dose escalation period, this structure was selected so that blood results will be available prior to additional study drug administration. Study adherence and symptom assessment visits will be conducted every 2 weeks at the first weekly HD treatment in the scheduled week (i.e. Monday or Tuesday during weeks 8, 10, 12, 14, 16, and 18). Hearing assessments will be conducted every four weeks at the first weekly treatment (i.e. Monday or Tuesday during weeks 10, 14, and 18). Urine sample visits will be conducted at the mid-week treatments of the 12th week and final week of the follow-up period (i.e. Wednesday or Thursday during weeks 12 and 18). All remaining study drug will be returned at the first weekly treatment (i.e. Monday or Tuesday) of week 19. A final pill count (adherence assessment) will be performed upon study drug return (week 19).

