6.1 Primary Endpoints

Short-term and longer-term efficacy- urine volume (assessed separately)

- Among participants with baseline 24-hour urine volume ≥200 mL: incidence of ≥25% increase in urine volume
- Among participants with baseline 24-hour urine volume <200 mL: incidence of a ≥50 mL increase in urine volume to a urine volume of at least 100 mL/24-hours

Short-term and longer-term safety- electrolytes (assessed separately)

- Incidence of serum potassium <3.2 mEq/L
- Incidence of serum magnesium <0.8 mg/dL
- Incidence of serum corrected calcium <7.0 mg/dL

Short-term and longer-term safety- furosemide levels

• Incidence of serum furosemide level >12 microgram/L

Short-term and longer-term safety- BP

 Incidence of dialysis-associated hypotension requiring hospitalization or treatment in an emergency room and not attributable to overt sepsis, acute myocardial infarction, or other cardiovascular event (e.g. aortic dissection)²¹

Short-term and longer-term safety- symptoms (assessed separately)

- Incidence of severe or very severe patient-reported rash, tinnitus, or hearing change) not attributable to causes
 other than furosemide
- Incidence of 10-point decrease in Inner EAR instrument score

Short-term and longer-term tolerability- symptoms (assessed separately)

• Incidence of severe or very severe patient-reported cramping, dizziness/pre-syncope, unusual tiredness/weakness, chest pain, nausea, vomiting, or diarrhea not attributable to causes other than furosemide

Short-term and longer-term acceptability

• Incidence of an affirmative response to the furosemide acceptance question

Short term- and longer-term adherence

• Incidence of participants having <20% of furosemide pills remaining at pill counts

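### The first furosemide dose is released without reference to the 24-hour urine volume measured at week -1, so a participant with measured anuria would be dosed as written

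*Combined protocol and SAP*

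**What the plan says.** - **Contraindication (1.2).** "Furosemide is contraindicated in patients with anuria and in patients with a history of hypersensitivity to furosemide".
- **Intended population (3.3).** "Our selection criteria exclude patients unlikely to respond to diuretics (i.e. minimal urine output", together with two other groups.
- **Entry test (3.4).** The only urine-output criterion is "Patient self-report of at least 1 cup urine/24-hours". Loop diuretic allergy is an exclusion. Neither anuria nor a measured volume appears in the list.
- **Measurement before dosing (4.2).** "In the one week prior to start (week -1), the following data will be obtained: serum electrolytes, 24-hour urine collection", plus symptom and hearing assessments.
- **First dose (4.3, week 0).** Item A reads "Participants who are not taking oral furosemide at study entry will receive 2-weeks supply of 80 mg oral furosemide twice daily dosing". Items B and C give people already on a loop diuretic their current furosemide dose or its equivalent. Prior loop diuretic use is the only thing that decides among the three.
- **Next measurement (4.1).** "Urine samples will be collected twice during the dose escalation period at mid-week treatment visits (i.e. Wednesday or Thursday during weeks -1 and 5". The week -1 sample is therefore the only urine volume available until week 5.
- **Primary efficacy endpoint (6.1).** For a baseline below 200 mL/24 h, response is "incidence of a ≥50 mL increase in urine volume to a urine volume of at least 100 mL/24-hours". The stratum has no lower limit.

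**The concern.** The plan names two contraindications. One became an exclusion criterion. The other rests on what the patient reports, although an objective measurement is taken before any study drug is handed out. That measurement defines the baseline for the primary endpoint, but it is not used to decide who is treated.

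The participants concerned have the least to gain and the least capacity to clear the drug: 1.2 says "Furosemide is predominantly excreted unchanged in the urine". The hemodialysis evidence cited in 1.3 shows a response at volumes down to 100 mL/day, and at doses above 1,000 mg/day, against a study maximum of 320 mg/day.

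There is also a consequence for the analysis. A participant whom 3.3 describes as excluded would be classified in the primary responder analysis, because 6.1 accepts any baseline below 200 mL.

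**Working it through.** The plan gives no figure of its own on this point, and the power calculation in 6.4 does not bear on it. The check sets the provisions side by side and works through the 6.1 rule.

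**1. Does any written provision tie the first dose to the week -1 volume?**

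| Provision | What it covers | Governs the first dose by urine volume? |
|---|---|---|
| 3.4 | Self-reported output | No; a low measured volume does not breach it |
| 4.3, week 0, A to C | Dose by prior loop diuretic use | No |
| 4.1 | Blood results available before titration | No; urine results are not mentioned |
| 3.5.3 | Escalation withheld for a contraindication; examples are hypokalemia and serious hypotension | No; escalation only, and urine volume is not named |
| 1.2, 1.3.1, 3.5.2, 4.3 stop events | Electrolytes, attributable side effects, blood pressure, non-acceptance | No; urine volume is not listed |
| 7.6.2 | Investigator reviews all results and notifies participants | No dosing rule |
| 9.2.1 | Investigator may end participation | Discretionary; urine volume is not named |

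A group A participant measured at 0 mL therefore starts 2 x 80 = 160 mg/day. This needs no definition of anuria in mL.

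**2. When does the 100 mL floor in 6.1 matter?** For baseline b below 200 mL, a responder needs a follow-up volume of at least max(b + 50, 100). The floor adds something only if b + 50 < 100, that is, b < 50 mL.

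| Baseline (mL/24 h) | Rise needed (mL) | Floor binds? |
|---|---|---|
| 0 | 100 | Yes |
| 25 | 75 | Yes |
| 49 | 51 | Yes |
| 50 to 199 | 50 | No |

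Taking one US cup as about 237 mL (a unit conversion that the documents do not give), everyone in the <200 mL stratum has measured less than the amount they had to report to enter.

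**3. Is the result available in time?** Wednesday of week -1 to Monday of week 0 is 5 days. The treatment-visit window is -4 to +4 days. Limited to dialysis sessions, the gap runs from 2 days (Friday of week -1) to 9 days (Friday of week 0). The Thursday/Tuesday schedule gives the same range.

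**4. How long until the next look?** Monday of week 0 to Wednesday of week 5 is 5 x 7 + 2 = 37 nominal days. The 3.5.3 clause could first apply at week 2. By then a group A participant would have been supplied 14 x 160 = 2,240 mg, if no other stop event intervened.

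**The case against.** **The contraindication clause in 3.5.3.** Its examples are open-ended and 1.2 names anuria, so an investigator could fairly read it as barring escalation in known anuria. That stands. A reader might infer that a participant with anuria would be carried to 320 mg/day with nothing in the plan to prevent it. The documents do not support that, so cumulative doses that assume full escalation do not measure the impact. The clause still does not reach the first dose.

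**The wording of 3.3.** The statement follows the self-report rule and can be read as describing it: someone who reports a cup a day is not minimal by that test. A single low collection may also be incomplete or atypical. Both points are fair. They argue for confirming a low result, not for leaving it without consequence.

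**The endpoint.** A reader might infer from the floor that the team meant to treat anuric patients. The documents do not say so. A responder rule has to cover every possible baseline, and the floor makes response harder to claim at very small volumes. What remains is that 6.1 sets no lower limit.

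**Safety monitoring.** Serum furosemide is measured at week -1 and weekly in weeks 1 to 6, and a level above 12 microgram/L is a primary safety endpoint. Symptoms are recorded weekly and Inner EAR every two weeks during escalation, with audiometry referral. Sections 1.3 and 1.3.1 regard hearing risk as low at these doses, and the remark in 1.3.1 on kidney impairment applies to every participant. This lowers the stakes. However, the furosemide level is not a stop event, and all these controls act after exposure.

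**Regulatory reading.** A reader might also infer that the IND-exemption reasoning in 1.2 fails. That text concerns the investigation as a whole, and nothing shows that anuric participants would be more than isolated cases.

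**Conclusion.** The point holds in limited form. A listed contraindication is not checked against the measurement that would reveal it before the first dose, and 3.3, 3.4 and 6.1 do not agree on how low a urine volume may be. The later safeguards are real, but they are partial, general or discretionary.

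The size is known for the individual and unknown for the trial. A group A participant measured at 0 mL starts 160 mg/day, and the next scheduled volume is 37 nominal days later. The documents do not give the share of people reporting one cup who would measure below 50 mL, so no count can be stated.

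The conclusion rests on reading the 4.3 release rules as complete. It does not rest on any definition of anuria, which the documents lack, nor on a claim that harm is likely at these doses. It is a correction worth making, not a flaw that undermines the study.

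**What to change.** 1. **3.4:** add an exclusion for confirmed anuria on the week -1 collection, with one stated limit. A limit of <50 mL/24 h is a reasonable example, because the 6.1 floor binds below that point, but it is an assumption that the team must own. A limit of 100 mL would also remove participants at 50 to 99 mL, which is a debatable change of population.
2. **4.3:** require the investigator to check that volume before releasing the first kit to group A, and before the week 2 increase in groups B and C, who until then continue an existing or equivalent dose. If the volume is below the limit, repeat the collection once, using the urine creatinine already measured as a completeness check. If confirmed, do not start or escalate study drug.
3. **3.5.3:** name anuria among the contraindications.
4. **3.3 and 6.1:** align both with the limit. At 50 mL the floor in 6.1 becomes redundant, since b + 50 is then at least 100. Section 6.1 should also say how a group B or C participant is counted if study drug was given before anuria was confirmed.

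The cost is a few sentences, an occasional repeat collection, and a possible short delay to week 0. Some consented people will not start. They can be replaced within the planned 40, which leaves 40 - 36 = 4 places above the goal, shared with dropout.
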